# 3.2 Study Duration, Enrollment and Number of Sites

#### 3.2.1 Duration of Subject Study Participation

16 days: 1 day for consent, fitting, and initial evlauation; 14 days for at home use, and 1 day for follow up.

# 3.2.2 Total Number of Study Sites/Total Number of Subjects Projected

The study will be conducted at approximately 1 investigative site in the United States. This site is the UNC Meadowmont ENT outpatient clinic.

Recruitment will stop when approximately 20 subjects are recruited. It is expected that approximately 22 subjects will be enrolled to produce 20 evaluable subjects.

# 3.3 Study Population

# 3.3.1 Subject Inclusion Criteria

- 1) Male or female age 18 years and older
- 2) Diagnosis of venous pulsatile tinnitus
- 3) Patient at UNC ENT Meadowmont Clinic

# 3.3.2 Subject Exclusion Criteria

- Increased presence of acid in the body or excessive blood alkalinity
- Open head injury (including in or around the eye) within the past six months
- Pseudotumor cerebri (false brain tumor)
- Presence of brain or spinal shunt
- Known seizure disorder
- Known airway obstruction
- Increased likelihood of blood clotting (coagulation)

- age <18
- unable to provide written consent,
- history of neurological deficits,
- previous cerebral infarction (blockage or narrowing in the arteries supplying blood and oxygen to the brain)
- severe head trauma
- medical contraindications to restriction of blood outflow via the internal jugular veins
- glaucoma (narrow angle or normal tension increased pressure in the eyes),
- hydrocephalus (increased fluid on the brain)
- recent penetrating brain trauma (within 6 months),
- known carotid hypersensitivity
- known increased intracranial pressure
- idiopathic intracranial hypertension
- known intracranial vascular malformation (e.g. aneurysm, arteriovenous malformation, cavernoma)
- central vein thrombosis
- not tolerating initial fitting of collar.
- Known pregnancy (this is not a direct contraindication but is being made out of an abundance of caution)
- Inability to speak or comprehend English (this pilot study does not have funding for translators)

# 4 STUDY PROCEDURES

# 4.1 Study Treatment Phase

Pre consent: identification of eligility according to inclusion/exclusion factors by chart review

# 4.1.1 Visit 1 (at Meadowmont ENT clinic visit)

- Explanation of Study
- Invitation to participate
- Consenting of participant
- Tinnitus intensity and quality of life scales through REDCAP
- Fitting of collar
- Evaluation of pain or discomfort
- 10 minute observation of patient with fitted collar
- Readministration of tinnitus intensity scale
- Education on collar use and misuse (emphasis on no more than 4 hours daily and only while awake
- Transfer of collar and materials to participant

# 4.1.2 Between Visit (at home) phase

Patient wears collar for <4 hours total while awake for symptomatic relief as needed

Patient reports daily average tinnitus intensity with and without collar, length of use, and any adverse events through REDCAP email/text link

Continues daily for 14 days

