# 3.1.3 At Home Use (2 weeks)

Through a REDCAP link to their email or mobile device, the participants will daily record length of time using collar, average tinnitus intensity with and without collar, and any discomfort/adversity with collar use for 14 days consecutively.

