# 5.2 Efficacy Evaluations

#### 5.2.1 Diagnostic Tests, Scales, Measures, etc.

- Primary endpoint: symptom relief
  - Tinnitus aural intensity scale before and after collar administration at each visit and once daily for with collar and without collar intensity
- Secondary endpoint: QOL Impact
  - Tinnitus Handicap Index (Once at beginning of study, once at end)
  - Patient Reported Outcome Measurement Information System (PROMIS) scales in depression, anxiety, physical function, and satisfaction
- Secondary endpoint: Temporality
  - Aural intensity scale submissions will be plotted and compared over time course of study
- Secondary endpoint: Homes vs. clinic use
  - Supervised tinnitus intensity scale measurements will be compared to at home measurements to evaluate if perception of symptomatic intensity varies with environment

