#### 6.3.2 Efficacy Analysis

The primary analysis will be based on an intention to treat approach and will include all subjects who complete the study.

The primary efficacy endpoint will be the change in tinnitus intensity with and without the collar, averaged within and across each patient's completion of the tinnitus scales. This means that there will be 16 paired collar and no collar measurements per patient, one at each clinic visit and one each day during the 14 day intervening period. The significance of this change will be evaluated using a unidirectional t-test.

Secondary endpoints will include the following:

- Temporality of symptom relief
  - Subjects with and without collar scores will be averaged for each day of the study, ANOVA testing will evaluate for the presence of a significant time component.
- Supervised vs. unsupervised use
  - The mean relief recorded at the first and second visit will be averaged and compared avross patients with the mean relief recorded during at home use using a bidirectional t test.
- QOL impacts
  - Evaluated for each scale using bidirectional t test

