#### 6.4 Sample Size and Power

For the principal endpoint, the tinnitus intensity scale ranges from 1-10. Assuming an average tinnitus intensity of 5 and a standard deviation of plus or minus 2 (such that 95% of the venous pulsatile tinnitus population has tinnitus intensity between 1 and 9). Intensity scale measurements will be averaged across individual submissions and across participants. With 16 paired evaluations per participant and 20 participants total, that creates 320 non collar tinnitus intensity measures.

Setting an alpha of p=.05 and a power of 0.8 (beta=0.2), we expect a minimum effect of a 1 point decrease between the no collar and collar measurements. To be conservative, we will preserve the 2 point standard deviation assumed for the baseline measure to apply to the collar relief measure. These parameters allow us to evaluate the viability of our sample size.

$$n_{g} \doteq (z_{lpha/2} + z_{eta})^{2} rac{\sigma_{1}^{2} + \sigma_{2}^{2}}{(\mu_{1} - \mu_{2})^{2}}$$

Where n is the number of analyses that will allow our minimum effect size to be significant Substitution lends us the following

 $\begin{array}{l} n_{\rm g} = (1.96 {+}~ 0.8416)^{2*} (2^2 {+} 2^2) / (2)^2 \\ n_{\rm g} = 15.86 \end{array}$ 

Not only is our overall study well in exceeding the number of intensity measurement differences needed to measure a significant effect; we will be able to assess the significant effect within each participant, given that each participant will complete both the with and without collar scales a total of 16 times. This gives our study strong internal and external validity.

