#### 9.4.2 Risk Assessment

#### Not Greater than Minimal:

- Psychological
  - Wearing the collar might be embarrassing for some patients. This is averted through a flexible at home protocol in which they are only asked to wear the collar on an as needed basis for symptomatic relief and report their efficacy. Patients will be allowed to withdraw from the study at any time.
- Confidentiality
  - Any study has potential consequences a breach of confidentiality, this study will avoid those consequences through maintenance of the data in a password protected REDCAP database accessible only to the research team, all of whom are HIPAA certified.
- Discomfort
  - The device is FDA approved for contact sports, and there are no adverse risks for the indicated population. However there is a possibility that patients will feel discomfort when wearing it. Care will be made to ensure the fitting is optimize the patient's needs. Possibility of mild discomfort if collar used incorrectly; this will be averted by counseling patients to not use the collar while sleeping and by fitting the collar correctly to the neck circumference of the subject at the initial visit.

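### Fourteen of the 16 primary pairs are daily averages with and without the collar, taken under as-needed wear and not matched in time, so the primary contrast can mix collar effect with tinnitus level in either direction; 16 pairs is a maximum

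*Combined protocol and SAP*

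**What the plan says.** Home wear is at the participant's discretion. Section 4.1.2 states "Patient wears collar for <4 hours total while awake for symptomatic relief as needed", and the risk assessment in section 9.4.2 says of participants that "they are only asked to wear the collar on an as needed basis for symptomatic relief and report their efficacy".

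The home measurement is one report a day: "Patient reports daily average tinnitus intensity with and without collar, length of use, and any adverse events through REDCAP email/text link" (section 4.1.2; sections 3.1.3 and 5.2.1 agree). No section says which hours the without-collar average covers, or ties the two scores to one wearing episode. At the clinic visits the two ratings are taken around a supervised fitting; at Visit 1 the second follows 10 minutes of observation (sections 3.1.2, 4.1.1 and 4.1.3).

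Section 6.3.2 states that "there will be 16 paired collar and no collar measurements per patient", one per clinic visit and one per home day, and averages them into the primary endpoint, tested with a one-sided t-test. For the clinic-versus-home comparison, "The mean relief recorded at the first and second visit will be averaged" and compared with mean home relief; section 6.2 lists this as an effect of medical supervision. Section 6.4 counts 16 paired evaluations for each of 20 participants, derives a requirement of 15.86, and concludes that "we will be able to assess the significant effect within each participant".

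**The concern.** If symptoms prompt wear, tinnitus level helps decide which hours are collar hours. The with-collar and without-collar averages then describe different parts of the day, and their difference contains more than the collar's effect.

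The study is a single unblinded cohort (Abstract, section 9.1). This contrast is its primary efficacy evidence and is meant to support a multicenter grant application (section 2). A bias against the collar could hide a modest real benefit; a bias in its favour could produce a positive one-sided test with no benefit at all. Length of use and an adherence item are collected (section 3.1.3; Surveys and Scales in section 1.3), but no described analysis links them to the primary contrast.

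As-needed wear also allows days without wear. Such a day has no with-collar value, and no rule covers it, yet sections 6.3.2 and 6.4 treat 16 pairs as assured.

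**Working it through.** **1. The plan's own figures.** Pairs per participant: 2 clinic + 14 home = 16, and 16 × 20 = 320. Section 6.4 uses 320 for the non-collar ratings; the matching maximum for pairs is also 320. The home share of the endpoint is 14/16 = 87.5%.

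Required number as printed in section 6.4: (1.96 + 0.8416)² × (2² + 2²)/2² = 7.849 × 8/4 = 15.70, close to the stated 15.86.

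**2. The within-participant claim.** The text of section 6.4 states a 1-point difference, but the substitution uses 2. With 1 point the same formula gives 7.849 × 8/1 = 62.8, so 63. A one-sided version gives 49.5, so 50. Both are far above 16, so the claim lacks support even with all 16 pairs.

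**3. Pairs under as-needed wear.** Let f be the share of home days with any wear. Pairs per participant = 2 + 14f.

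| f (assumed) | Pairs per participant | Total for 20 |
|---|---|---|
| 1 | 16 | 320 |
| 0.75 | 12.5 | 250 |
| 0.5 | 9 | 180 |
| 0 | 2 | 40 |

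At 90% wear with independent days, 0.9^14 = 0.23 of participants would have all 16.

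Group precision: SE = √((τ² + ω²/k)/20), where τ is the between-participant SD of relief, ω the within-participant SD of a single difference and k the number of pairs. Going from k = 16 to k = 9 raises the SE by 2.3% (τ = 2, ω = 2), 7.5% (1, 2) or 12.2% (1, 2.83). These values are assumed.

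**4. Size of the timing bias.** The documents give no within-day variation, so all inputs here are assumptions: 16 waking hours, hourly normal intensities with autocorrelation 0.5, a collar with no effect, and 200,000 simulated days. Endpoint bias = home bias × 14/16. That factor supposes wear on all 14 days; at 70% or 50% of days it becomes 9.8/11.8 = 0.83 or 7/9 = 0.78.

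| Pattern of wear and recall | Hours worn | SD 1 | SD 0.5 |
|---|---|---|---|
| Wear from the loudest hour; without-collar score = all other hours | 1 | 1.51 against | 0.76 against |
| Same | 2 | 1.05 against | 0.53 against |
| Same | 4 | 0.61 against | 0.31 against |
| Wear starts the hour after the loudest; without-collar score = all other hours | 4 | 0.05 against | 0.03 against |
| Wear after the loudest hour; without-collar score = level in that hour | 1 to 4 | 0.97 to 1.25 in favour | 0.49 to 0.63 in favour |

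The 0.61 lies between 0.55 and 0.70, depending on how starts late in the day are handled. A true 1-point benefit would show as about 1 − 0.61 = 0.39 in the 4-hour case at SD 1.

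A separate simulation of the whole endpoint used 20 participants, 3 hours of wear, autocorrelation 0.7 and no collar effect. Wear unrelated to tinnitus level gave about 0. Wear in the loudest hours gave −0.61 (SD 0.5) and −1.23 (SD 1). Recall of the pre-wear peak gave +0.47 and +0.93, and the one-sided test rejected in all 400 runs at each SD.

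**5. Check on the proposed remedy.** Two ratings 10 minutes apart keep some regression to the mean: 1 − 0.5^(10/60) = 0.109 of the starting elevation. Onset in the loudest quarter of hours (mean 1.271 SD) leaves 0.07 (SD 0.5) to 0.14 (SD 1) points in the collar's favour; a 1.77 SD peak leaves 0.19 at SD 1.

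The supervised-visit 95% interval has half-width 2.093 × SD/√20 = 0.47, 0.94 or 1.32 for an assumed SD of participant mean relief of 1, 2 or 2.83.

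**The case against.** The strongest reply is that the bias figures are assumptions throughout. If intensity is nearly constant within a day, the mismatch is harmless, and the near-complete relief hypothesised in the introduction would remain visible. This stands, and it is why the point concerns what the contrast can mix, not a demonstrated bias.

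The plan already compares clinic with home relief, and the clinic pairs are taken close together. A gap between them would flag a problem. That stands in part: the comparison would attribute the gap to supervision, and it does not correct the primary result.

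Table 1 heads the home phase as daily for 14 days, and section 7.1.2 puts adherence reminders in the daily scales. The heading may refer to reporting, and sections 4.1.2 and 9.4.2 both make wear as needed. The forms are not part of these documents (Appendix), so they may define the without-collar average or offer a not-worn response; this cannot be seen.

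A reader might infer that the bias must run against the collar because people wear it when symptoms are loud. The documents do not support a fixed direction: recall of the pre-wear level reverses the sign with similar size. A reader might also infer that missed wear days are what defeats the within-participant claim, by taking 16 pairs to 15. That comparison relies on 15.86, which rests on the wrong difference.

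**Conclusion.** The concern holds as a weakness that should be addressed. Under as-needed wear, 87.5% of the planned primary pairs are contrasts between averages that nothing matches in time, so the primary result can mix collar effect with tinnitus level. Under the stated assumptions, the bias ranges from near zero to more than the planned 1 point in either direction at a within-day SD of 1, and is about half that at 0.5. A false positive is as much a possibility as an understated benefit. It would go too far to call the primary result invalid: the documents give no within-day variation, and the clinic pairs and the quality-of-life scales do not depend on the home pairing.

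The figures of 16 pairs per participant and 320 in total are maxima. It would also go too far to say that days without wear threaten the group analysis, since the standard error rises only about 2% to 12% from 16 to 9 pairs. The within-participant claim in section 6.4 is unsupported whatever the wear pattern, because the stated 1-point difference needs about 63 by the plan's own formula.

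**What to change.** Leave the wear rules and the primary endpoint as they are; the daily averages address sustained relief at home, which the Abstract names as a main outcome.

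1. Report the supervised-visit contrast with its 95% confidence interval beside the overall primary result.
2. Add to the daily form two ratings tied to one wearing episode: one just before the collar goes on, and one shortly after while it is still worn (10 minutes would match Visit 1). Analyse them as a sensitivity analysis of the home contrast.
3. In sections 6.3.2 and 6.4 write up to 16 pairs, state that a day without wear yields no pair, and report pairs per participant. Remove from section 6.4 the claim that a significant effect can be assessed within each participant.

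The cost is a few text edits and two short ratings per wearing day, some of which will be missed or filled in from memory. The new ratings keep a small regression-to-the-mean bias in the collar's favour (about 0.07 to 0.19 points under the assumptions above) and do not remove expectation effects in an unblinded study. The supervised-visit interval will be fairly wide with 20 participants. The onset ratings have to be collected during the study, as they cannot be recovered afterwards.

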#### 4.1.3 Follow up visit

Reevaluation of tinnitus baseline without collar and with collar under medical supervision

Collection of collar and instruction materials

QOL surveys through REDCAP

Qualitative Exit Survey on collar

# 4.2 Subject Completion/Withdrawal

Example: Subjects may withdraw from the study at any time without prejudice to their care. They may also be discontinued from the study at the discretion of the Investigator for lack of adherence to study treatment or visit schedules, development of exclusion criteria, or adverse events The Investigator or the Faculty Advisor may also withdraw subjects who violate the study plan, or to protect the subject for reasons of safety or for administrative reasons. It will be documented whether or not each subject completes the clinical study. If the Faculty Advisor becomes aware of any serious, related adverse events after the subject completes or withdraws from the study, they will be recorded in the source documents and on the CRF.

#### 4.2.1 Early Termination Study Visit

Subjects who withdraw from the study will have all records deleted from the REDCAP database except for adverse events, which will be reported by the Faculty Advisor to the IRB.

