Study Phases Enrollment Study Treatment Follow-Up	
 
Participants meeting inclusion/exclusion criteria at UNC
 
Meadowmont will be invited to participate. Those who consent will be fitted with the collar. Then, the at home treatment phase will begin where they report on collar efficacy. Finally, a follow up visit will be conducted to complete exit surveys.
 
	
Efficacy Evaluations	Significant improvement in tinnitus symptoms while wearing collar.	
Safety Evaluations	At intiial visit, team clinician will supervise collar fitting and evaluate for significant pain, discomfort, or adverse effect which will halt participation for that participant and be recorded. During at home study phase, participants will report any adverse effects with their daily recording of symptomatic efficacy.	
Statistical And Analytic Plan	One sided t test on tinnitus intensity while wearing collar vs. while not wearing collar will evaluate primary endpoint of collar relief efficacy. ANOVA analysis of intensity differences will elucidate effect of time, if any. One sided t test will evaluate secondary endpoints of quality of life	
DATA AND SAFETY MONITORING PLAN	Faculty mentor [name] is monitoring all safety related aspects. These include the evaluation of the initial collar fit, collar use education, and reporting of adverse events during at home period.	

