# 5.3 Safety Evaluation

Example: Subject safety will be monitored by observation and intervention of adverse events during the physician-supervised fitting period at the beginning of the study and by education of the participants to discontinue use of the collar with any significant change in physical well-being or onset of new symptoms and immediate reporting of that occurrence to the PI and Faculty Advisor through the REDCAP link.

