# 6.3.3 Safety Analysis

Adverse events are not expected; however, all subjects entered into the study at Visit 1 will be included in the safety analysis. The frequencies of AEs by type, body system, severity and relationship to study drug will be summarized if at all present. SAEs (if any) will be described in detail.

AE incidence will be summarized along with the corresponding exact binomial 95% twosided confidence intervals.

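### Section 4.2.1 schedules no early termination visit and deletes the withdrawn participants' non-AE records that the safety analysis in 6.3.3 and the completion record in 4.2 need

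*Combined protocol and SAP*

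**What the plan says.** Despite its heading, section 4.2.1 contains one sentence. It states that "Subjects who withdraw from the study will have all records deleted from the REDCAP database except for adverse events", and of those events it adds "which will be reported by the Faculty Advisor to the IRB". It gives no visit, assessment or device-return step, and Table 1 has no early termination column.

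Other sections bear on the same participants:

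- **Safety analysis (6.3.3).** All participants entered at Visit 1 are included. "The frequencies of AEs by type, body system, severity and relationship to study drug will be summarized", and incidence is to carry exact binomial 95% intervals.
- **Withdrawal (4.2).** Adverse events and development of exclusion criteria are grounds on which the investigator may discontinue a participant. Whether each participant completes must be documented. Later capture is limited: "If the Faculty Advisor becomes aware of any serious, related adverse events after the subject completes or withdraws from the study", these are recorded.
- **Collar.** Visit 1 ends with "Transfer of collar and materials to participant" (4.1.1). The only collection step is in 4.1.3, at the follow-up visit: "Collection of collar and instruction materials".
- **Symptoms at home (5.3, 7.1.3).** Participants are taught to "discontinue use of the collar with any significant change in physical well-being or onset of new symptoms" and to report at once to the PI and Faculty Advisor.
- **Data (3.1.3, 4.1.2, 9.2).** Daily length of use is entered through a REDCap link, and all study data are held in REDCap.

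**The concern.** People who leave a device study early include those who leave because of a symptom. They are few, but their data carry much of the safety information. The plan keeps their AE entries and discards the records around them: how long the collar was worn and on which days, baseline history as held in the study database, and possibly the fact of enrolment and the reason for leaving.

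Two parts of 6.3.3 are exposed. Relationship to the device is judged largely from timing and exposure, and wear time is the only exposure measure collected. The binomial intervals need a denominator that includes leavers who had no event, and it is exactly those people who have no record left under 4.2.1.

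The same section is also where a reader would look for what happens to the collar, and to an unresolved event, when someone leaves during the home phase. It does not say. This matters because section 1.1 describes the collar as raising intracranial pressure, safely in the protocol's words, and because the pilot is meant to support a multicenter grant application (section 2).

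**Working it through.** The plan gives no figure on this point to reproduce. The check sets the passages side by side and then sizes the effect on the denominator.

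**1. What survives for a participant who leaves in the home phase, if 4.2.1 is followed as written**

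| Item | Needed by | Held in | After 4.2.1 |
|---|---|---|---|
| AE entry | 6.3.3 | REDCap | Kept, reported to the IRB |
| Daily length of use | Relationship, 6.3.3 | REDCap only (3.1.3, 4.1.2, 9.2) | Deleted |
| Medical history | Relationship, 6.3.3 | REDCap; also clinic record in EPIC | REDCap copy deleted, clinic record remains |
| Entry at Visit 1, no event | Denominator, 6.3.3 | REDCap; signed consent form | REDCap record deleted |
| Completion status | 4.2 | Location not stated; 9.2 puts all data in REDCap | Deleted if held there |

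Deletion of length of use follows directly from the text. The denominator and completion status are at risk but could be rebuilt from consent forms or source documents if someone plans to do so.

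**2. Who is affected**

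- Halted at the Visit 1 fitting: the synopsis provides for "significant pain, discomfort, or adverse effect which will halt participation for that participant and be recorded". In 4.1.1 the collar is handed over last, so this person has none to return.
- Stops wearing the collar but stays in the study (5.3): not a withdrawal. Daily reports continue and the collar is collected at the follow-up visit.
- Withdraws, or is discontinued, after Visit 1: 4.2.1 applies, no closing contact is scheduled, and no return step is listed.

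Only the third group meets the whole problem. The deletion rule may also reach the first group if they count as withdrawn, but they have no home wear time to lose.

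**3. Size**

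Inputs from 3.2.2: 22 enrolled, 20 evaluable. Implied non-evaluable: (22 − 20)/22 = 9.1%. Reasons and timing are not stated. Assume, as the upper end, that both are event-free withdrawals whose records are deleted; the lower end is none.

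- No events: exact two-sided upper limit = 1 − 0.025^(1/n). For n = 22, 1 − 0.025^(1/22) = 15.4%. For n = 20, 1 − 0.025^(1/20) = 16.8%.
- One event in a completer: 1/22 = 4.5% (Clopper-Pearson 0.1% to 22.8%) against 1/20 = 5.0% (0.1% to 24.9%).

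The interval shifts by about 1 to 2 percentage points at its upper end, slightly overstating incidence. This is minor beside the interval's width. The loss of wear time is not a matter of percentage points: it falls on each leaver, including any whose event prompted the exit.

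**4. AE follow-up**

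Table 1 marks AE rows at Visit 1 and during home use, but not at the follow-up visit. No section specifies following an event to an outcome, and 6.3.3 does not list outcome among the variables to summarise. This gap therefore touches completers as well.

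**The case against.** The best defence is that safety reporting does not stop at withdrawal. New symptoms are to be reported at once, reported AEs are retained and go to the IRB, everyone from Visit 1 is in the safety analysis, and later serious, related events are recorded if they become known. Severity and relationship could be judged when the event is reported, and clinic records lie outside REDCap. The consent pages are not available here, and the Appendix says further documents went to the IRB, so device return or data retention may be covered there. The heading may also be template residue, since 4.2 still carries the word Example.

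Much of this stands, and it rules out stronger readings that a reader might infer:

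- That participants who stop because of symptoms keep the collar. The plan does not say so. Stopping use is not withdrawal, those halted at fitting never take a collar home, and for the rest the text is silent.
- That their events go unreported or cannot be assessed. The AE entries survive, and their content is not defined. Assessment is weakened, not prevented.
- That two collars or two events will be lost. The 2 of 22 carries no reasons and may include fitting failures.

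What the defence does not answer is the deletion rule. It is an explicit instruction, it removes the only wear-time record, and it sits against 6.3.3 and 4.2. A consent form could not restore data that the protocol tells staff to delete.

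**Conclusion.** The point holds as a conflict between a stated deletion rule and the stated safety analysis, together with a visit heading that has no visit under it. It should be corrected, but it does not undermine the trial. For home-phase leavers, wear time is lost and relationship to the collar is harder to judge; event-free leavers may drop out of the denominator, with a small effect on the interval.

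This rests on three assumptions: that 4.2.1 is carried out literally, that length of use is held nowhere but REDCap, and that at least one participant leaves after Visit 1. On device return and AE follow-up, the finding is only that no step is listed for early leavers in the text available, and that the relevant sections need to be reconciled.

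**What to change.** Amend 4.2.1 so that data collected up to withdrawal that the safety analysis needs are retained: enrolment and completion status, reason for stopping, length of use, relevant medical history and AE records. State this in the consent.

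Add one closing contact for anyone who leaves early, which the participant may decline, to record the reason for stopping, any adverse events and the status of any event still open. Show it in Table 1.

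Reconcile 4.1.3, 4.2, 4.2.1, 5.3 and Table 1 on device return and on AE follow-up for early leavers. What those steps should be is for the investigators and clinicians to decide.

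The cost is one extra contact for a small number of participants, about 2 if the 3.2.2 margin is all early leavers, and a sentence in the consent. The drawback is a further approach to someone who has chosen to leave, which is why it must be optional.
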